3.1.3 Reports for which this Statistical Analysis Plan applies

This analysis plan shall apply to the final report. Statistical analysis for study related publications will not be limited to this plan. However, it is the intent that the main study publication will follow the methods detailed in this plan, which in some cases supersede the investigational plan.

3.2 Primary Objective: Appropriate Therapy

The primary objective is to demonstrate that appropriate VT/VF therapy rates (shock and ATP) for subjects meeting 1.5 prevention criteria implanted with a Medtronic device (ICD/CRT-D) are equivalent (within 30%) to rates in subjects meeting secondary prevention criteria.

The primary objective will be evaluated by using post-implant time to first appropriate VT/VF therapy (shock and ATP). More specifically, the following hypothesis will be tested:

Hypothesis

H_0 : Hazard ratio of Implanted 1.5 patients to implanted secondary patients ≤ 0.70
 H_a : Hazard ratio of Implanted 1.5 patients to implanted secondary patients > 0.70

Endpoint Definition

The event of interest for this objective is appropriate VT/VF therapy. To qualify as an event, a VT/VF event observed by the ICD/CRT must be adjudicated to be one of the following by the Episode Review Committee:

- Polymorphic VT/VF
- Monomorphic VT
- Non-sustained VT/VF
- Other VT/VF, specify:

Additionally, the episode must have been treated either by ATP, shock, or both by the device.

Performance Requirement

The null hypothesis will be rejected if the one-sided 95% lower confidence bound of the hazard ratio of implanted 1.5 subjects to implanted secondary prevention subjects is greater than 0.70.

Analysis Methods

A Cox proportional hazard model will be used to compare the hazard rates of first appropriate VT/VF therapy between implanted subjects meeting 1.5 prevention criteria and secondary prevention subjects. Because secondary and 1.5 patients are known to be different in many potential covariates, the Cox proportional hazards model will not include any covariates. The one-sided hypothesis test will be performed by computing a 90% two-tailed confidence interval for the hazard ratio between the groups and using the lower limit of this estimated 90% CI as a rejection boundary of the null hypothesis. In particular, if the 90% CI lower limit is greater than 0.7 then the null hypothesis will be rejected.

The analysis will be performed using SAS code similar to:

```
proc phreg data = alldata;
  where group in ('A','C');
  class group (ref = 'A');
  model time2event*eventStatus(0)= group/ rl alpha = 0.1;
  run;
```

Additionally, Kaplan-Meier estimates of the survival curves will be displayed for each prevention criteria group.

Determination of Patients/Data for Analysis

- All 1.5 prevention and secondary prevention subjects with an ICD/CRT-D implant and at least one device interrogation available in the database will be included in the primary analysis hypothesis test. This includes subjects implanted with a device after the initial enrollment period. These later implants will be included if they are secondary or 1.5 at the time of implant.
- Time 0 is the implant date and, if no events occur, subjects will be censored on the date of their latest device interrogation.
- VT/VF episodes that cannot be adjudicated (due to not saving full episode data or any other reason) will be ignored. Often, these episodes are followed by episodes that can be adjudicated, and since the endpoint is time to first episode, effects on the results from these events will be minimal. In addition, these should be balanced between the comparison groups.

Sample Size Calculation

The minimum required sample size for this study has been estimated to be 4800 subjects based on the following:

- 60% of enrollments will be secondary prevention and 40% primary prevention
- 50% of primary subjects will be in the 1.5 group
- 57% of secondary subjects will get an ICD (includes CRT-D)
- 45% of 1.5 subjects will get an ICD
- 22% of 1.0 subjects will get an ICD
- Annual attrition (includes exits and deaths) will be 10%
- The study will end two years after the last enrollment
- 4000 patients will take 2 years to enroll with enrollment beginning slowly, and then accelerating to a steady 246 per month
- Expected rates of appropriately treated VT/VF in secondary subjects follow Figure 2, with a higher rate in the first year (22.5%), then a constant rate (11.1%) thereafter
- The hazard ratio of 1.5 to secondary is 0.91

Under the above assumptions and using the hypothesis test stated above, 4800 subjects will have 80% power to reject the null hypothesis. With 4800 enrolled patients, it is expected that approximately 1650 secondary prevention subjects will be implanted, 430 1.5 prevention subjects will be implanted, and 200 1.0 subjects will be implanted.

More details, including the simulation program can be found in the Appendix.

Sample Size Re-estimation

Because most of the assumptions above are based only on investigator opinion, the sample size will be re-estimated during the study using the same simulation methods, but changing the following assumptions using the study data:

- % of enrollments will be secondary prevention
- % of primary patients in the 1.5 group
- % of secondary patients who will get an ICD (includes CRT-D)
- % of 1.5 patients who will get an ICD
- % of 1.0 patients who will get an ICD
- Annual attrition (includes exits and deaths)
- Enrollment rate

With this re-estimation of sample size, the length of follow-up after the last enrollment may be changed as well. Because no comparisons will be done at the point of re-estimation, alpha is not affected and the final analysis can compare the p-value to a 0.05 alpha level.

The sample size re-estimation will occur at the later of:

- One year after the 400th subject has been enrolled
- The time of the 2000th enrollment.

The database will be frozen for the sample size re-estimation with a visit cut-off date of 4 weeks after the 2000th enrollment, and an enrollment cut-off of the date of the 2000th enrollment. That will allow collection of 1.5 Criteria and implant/implant refusal data for the last subjects enrolled prior to the enrollment cut-off. The enrollment cut-off means any subject consented after that date will not be included in analysis.

Subjects who meet the “excluded” criteria in section 3.1.2 will not be included in the sample size re-estimation calculations. This will mean less than 2000 subjects will be included. Additionally, the new sample size will add subjects to replace the excluded subjects. For example, if 1900 subjects are not

excluded at the time of database freeze and the sample size re-estimate calls for 3000 subjects, then 1100 more non-excluded subjects will need to be enrolled in the study.

It is the study sponsor's discretion to increase (to a maximum of 8000 subjects) or decrease the sample size, or increase or decrease the length of follow-up after last enrollment.

If fewer subjects are required, the study sponsor may either lower the sample size, or increase the power of the study (possibly keeping the original sample size). If more subjects are required, the study sponsor may elect to not increase the sample size, but may increase the length of follow-up to ensure adequate power for the study.

Study sites will be notified of any change in sample size and length of follow-up (if applicable) at that time. The investigational plan will not be changed.

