6.10 Subject Follow-up Visits

Subjects should have a scheduled follow-up visit every 6 months post-implant (Arms A, C, and E) or implant refusal (Arms D, and F) until study closure, subject exit or death, with the exception of secondary prevention subjects who do not receive an implant (Group B); these subjects will be exited following implant refusal (Figure 1).

After completion of the Implant/Implant Refusal eCRF, Medtronic will provide the target dates and windows for each visit to the implanting site. Perform scheduled follow-up visits every 6 months according to Table 9. Follow-up visit windows are based on days post-implant. If a subject is seen beyond their 60-month visit, windows will continue on the same pattern with a width of 120 days. Should a subject visit fall outside the pre-specified window, a study deviation must be reported and the original follow-up schedule maintained for subsequent visits.

Data analyses will include follow-up visits, regardless of whether the visits occur within the time window. Therefore, a late visit is preferred over a missed visit but must be accompanied by a deviation.

Table 9: Follow-up windows

Study Follow-up Visit	Window (Calculated days post-implant)		
	Window Start (days post-implant)	Target (days post-implant)	Window End (days post-implant)
6 month	123	183	243
12 month	305	365	425
18 month	488	548	608
24 month	671	731	791
30 month	853	913	973
36 month	1036	1096	1156
42 month	1218	1278	1338
48 month	1401	1461	1521
54 month	1584	1644	1704
60 month	1766	1826	1886

Complete a Subject Contact CRF for each follow-up visit. If more than one visit (contact) occurs during a window, complete an additional unscheduled Subject Contact visit CRF.

During follow-up visits, information will be collected on the subject's vital status and use of Amiodarone, and subjects with an implanted device will have the device interrogated, either in office or via CareLink. Subjects who have access to CareLink will be asked to transmit data every 3 months when possible, and will not be required to do an in-person visit.

At 6-months post-implant, EQ-5D will be assessed again for all 1.5 subjects, regardless of implant status. Instructions for administering this test over the phone will be provided.

At approximately 22 months past the final enrollment, centers will be notified that study closure is about to occur and that they should attempt to make one final study contact with each subject to maximize overall study follow-up.

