6.11 Device Change

A Device Change eCRF will be completed if one of the following occurs:

- Device is explanted, and replaced (e.g., device reaches end of life, device upgrade)
- Device is explanted, and not replaced

- New ICD/CRT-D device implant (i.e., subject initially refuses an implant [baseline], but later decides to have a device implanted)
 - In this case, complete the 1.5 Criteria section of the Device Change eCRF.
- Device is permanently disabled and not replaced.

If a new device is implanted during a device change, a device interrogation should be performed prior to explant (in the instance of a device replacement) and again after new device implant. System information (e.g., device manufacturer) will be collected for the new device. Subject follow-up visit windows will not change following a Device Change, even if the device is explanted and not replaced.

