12.2.4 Analysis Methods

The hypothesis will be tested using a Cox proportional hazards model with survival time and first appropriate VT/VF episode as the dependent variable and group (secondary or 1.5) as the independent variable. A 95% one-sided lower confidence bound for the hazard ratio and a p-value will also be calculated. The data will be presented in a format similar to the right panel of Figure 2.

Adequate power is needed to perform the hypothesis test. Without adequate power, a non-significant test has little meaning. Therefore, the hypothesis test will not be performed and a p-value will not be calculated if there are fewer than 400 subjects in the implanted 1.5 prevention group. In that case, event rates and confidence intervals will be presented.

Time 0 will be the implant date and subjects will be censored on the date of their latest device interrogation. Only spontaneous, appropriately treated VT/VF episodes as adjudicated by the episode review committee will count toward the endpoint.

VT/VF episodes that cannot be adjudicated (due to not saving full episode data or any other reason) will be ignored. Often, these episodes are followed by episodes that can be adjudicated, and since the endpoint is time to first episode, effects on the results from these events will be minimal. In addition, these should be balanced between the comparison groups.

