proc mianalyze parms(classvar=ClassVal) = coxReg_fcs;
class SEXCHAR CMYISCH LBBB NYHA0 DIABETES CRIT15SYNC CRIT15NSVT CRIT15PVC
GROUP;
modeleffects AGE SEXCHAR QRS CMYISCH LBBB NYHA0 DIABETES LVEF0 CRIT15SYNC
CRIT15NSVT CRIT15PVC GROUP ;
run;

```

Kaplan-Meier estimates of the survival curves will be displayed for each group.

The same analysis will be performed comparing implanted and not implanted 1.0 subjects.

Time to Event Considerations

- Time 0 is the enrollment date and subjects will be censored on the last date they were confirmed to be alive.
- Non-implanted patients that later decided to implant the ICD/CRT-D, will have their time to event censored at the day of the implant procedure.
- Implanted patients that explanted the device (without replacement) will continue to be followed as part of the implanted group. These cases will be rare, and unless the explant is completely voluntary (i.e., not due to infection, or imminent subject end-of-life), censoring subjects at explant would bias the results in favor of implant. This is an intention-to-treat approach.
- Patients that had heart transplant will have their time to event censored at the day of the transplant.

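### The primary analysis does not stop at-risk time when a device left in place is permanently disabled, so it can count follow-up in which no event is possible

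*SAP*

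**What the plan says.** The primary endpoint is time to first adjudicated VT/VF that the device treated. SAP 3.2 requires this: "Additionally, the episode must have been treated either by ATP, shock, or both by the device". For everyone without an event there is one censoring rule: "Time 0 is the implant date and, if no events occur, subjects will be censored on the date of their latest device interrogation". Protocol 12.2.4 agrees: "Time 0 will be the implant date and subjects will be censored on the date of their latest device interrogation".

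Protocol 6.11 lists the situations that call for a Device Change eCRF. One is: "Device is permanently disabled and not replaced". The same section adds: "Subject follow-up visit windows will not change following a Device Change, even if the device is explanted and not replaced". At follow-up, under Protocol 6.10, "subjects with an implanted device will have the device interrogated, either in office or via CareLink"; no exception is made for a disabled device. Disablement is neither a listed reason for study exit (Protocol 6.12) nor a listed exclusion from analysis (SAP 3.1.2).

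The SAP deals with loss of the device only for mortality, in 3.3: "Implanted patients that explanted the device (without replacement) will continue to be followed as part of the implanted group". Section 3.2 has no counterpart. The Chagas therapy analysis, printed after SAP 3.3.2, repeats the primary censoring rule.

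**The concern.** Once its VT/VF therapies are permanently off, a device cannot deliver the ATP or shock that defines an event. If it stays in the body and is read at later visits, the last interrogation falls after that point. The subject then sits in the Cox risk set with a hazard that is zero by construction. As an illustration, a subject disabled at month 6 and last interrogated at month 24 adds 18 months of this kind.

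Such time lowers the apparent hazard in whichever arm has more of it. If that is the secondary arm, the 1.5-to-secondary ratio rises towards a non-inferiority finding and the one-sided error increases. If it is the 1.5 arm, the ratio falls and power is lost. The arms are not randomized and the primary model is unadjusted, because the SAP regards the groups as known to differ in many covariates. Equal disablement therefore cannot be taken for granted.

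**Working it through.** **Inputs from SAP 3.2 and the SAP appendix.** 4800 enrolled; 60% secondary; half of primary subjects in the 1.5 group; 57% of secondary and 45% of 1.5 subjects implanted; secondary-arm event probability 22.5% in year 1 and 11.1% per year after; hazard ratio 0.91; attrition 10% per year; 2.24 years of enrolment and 2 years of follow-up. Non-inferiority is declared if log(HR) − 1.645 × SE > log(0.70).

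**Plan's own figures.**
- Implanted secondary: 4800 × 0.60 × 0.57 = 1642 (plan: about 1650).
- Implanted 1.5: 4800 × 0.40 × 0.50 × 0.45 = 432 (plan: about 430).
- Re-implementing the appendix program with 10,000 runs gives 80.8% power and mean HR 0.903 at 4800 enrolled (plan: 80.4% and 0.903), and 73.7% power at 4000 (plan: 73.6%). There are about 663 events, of which 129 are in the 1.5 arm.

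**Added assumption.** The documents give no disablement rate. I assumed constant annual rates of 0.5% to 5%, unrelated to arrhythmia risk, with every disabled device still interrogated to the end of follow-up. No event is possible after disablement. The SAP rule and the fix (censor at the earlier of the existing censoring date and disablement) were applied to the same simulated trials.

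With equal rates of 0.5%, 1%, 2% and 5% per year, the share of counted person-time falling after disablement is 0.7%, 1.4%, 2.7% and 6.6%.

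**Planned effect** (4,000 runs each; Monte Carlo SE of power √(0.8 × 0.2/4000) ≈ 0.6 points):

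| Annual rate, secondary / 1.5 | Mean HR, SAP rule | Mean HR, fix | Power, SAP rule | Power, fix |
|---|---|---|---|---|
| 0.5% / 0.5% | 0.9036 | 0.9035 | 79.9% | 80.0% |
| 1% / 1% | 0.9034 | 0.9033 | 80.6% | 80.8% |
| 2% / 2% | 0.9056 | 0.9053 | 81.0% | 81.1% |
| 5% / 5% | 0.9065 | 0.9059 | 80.9% | 81.1% |
| 2% / 1% | 0.914 | 0.904 | 84.1% | 81.3% |
| 1% / 2% | 0.891 | 0.901 | 75.4% | 78.4% |
| 5% / 1% | 0.945 | 0.906 | 90.1% | 80.4% |
| 1% / 5% | 0.867 | 0.904 | 66.5% | 79.7% |

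**True hazard ratio 0.70** (6,000 runs each; Monte Carlo SE about 0.3 points, 0.4 at 11.2%):

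| Annual rate, secondary / 1.5 | One-sided error, SAP rule | One-sided error, fix |
|---|---|---|
| none | 4.8% | 4.8% |
| 1% / 1% | 5.2% | 5.1% |
| 5% / 5% | 5.2% | 5.2% |
| 2% / 1% | 6.6% | 5.4% |
| 1% / 2% | 4.4% | 5.3% |
| 5% / 1% | 11.2% | 5.0% |

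With equal rates the ratio moves by less than 0.001 at the planned effect. At a true 0.70 it moves by 0.0015 at most (5% per year: 0.7026 against 0.7011).

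**Check against a shortcut.** If the hazard were constant, the ratio would shift by (1 − share in the 1.5 arm)/(1 − share in the secondary arm). For 5% / 1%, using the shares above, that is (1 − 0.014)/(1 − 0.066) = 1.056. The simulation gives 0.945/0.906 = 1.043. The shortcut overstates the shift, because post-disablement time accrues late, when the assumed event rate has roughly halved.

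**The case against.** The strongest reply is that the case is inferred. Protocol 6.11 does not define permanent disablement or say that such a device is still read. If it cannot be read, the existing rule already stops the clock near disablement. That stands: the gap exists only for a disabled device that stays in place and is interrogated again. The visit and interrogation rules imply this without stating it.

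Second, no rate is given, and the SAP calls explant without replacement rare. Nothing in the documents says that disablement differs by arm, and equal rates do almost no harm. This stands too, and it keeps the point minor.

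Third, Protocol 12.2.1 aims at the rate over observed post-implant time, so counting all of it could be called a choice of estimand. This has some weight, but neither document presents it as a decision about disabled devices.

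A reader might also infer that explanted subjects go on accruing event-free time, since the mortality analysis keeps them in the implanted group. The documents do not support that. The mortality rule belongs to an endpoint censored at the last date known alive. In the primary analysis an explanted device gives no later interrogation, so explant without replacement is in effect already censored.

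**Conclusion.** The gap is real and minor. As written, the rule counts at-risk time in which the endpoint cannot occur, for subjects with a disabled device that is still interrogated. At assumed rates of 2% and 1% per year, the cost is about 1.2 points of one-sided error (6.6% against 5.4%) if the secondary arm has the higher rate, or 3.0 points of power (75.4% against 78.4%) if the 1.5 arm does. These figures rest on assumed rates, on disablement unrelated to arrhythmia risk, and on continued interrogation of every disabled device.

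A reader might conclude that the primary test is anti-conservative, or quote the 11.2% error. The documents do not support either. They give no rate and no direction, and 11.2% needs 5% per year in one arm against 1% in the other, which is a hypothetical extreme.

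**What to change.** Add one sentence to SAP 3.2 and to the Chagas therapy analysis: *subjects without an event are censored at the earlier of the latest device interrogation and the date of permanent disablement of VT/VF therapies recorded on the Device Change eCRF.* Explant without replacement may be named for clarity, although it changes little. Define permanent disablement for this purpose. Confirm that the eCRF carries its date, since the protocol names the form but does not list that field. Report the number of cases and the person-time affected by arm.

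Keep the present rule as a sensitivity analysis. The main downside of the change is that disablement may be related to prognosis, so censoring there may be informative. Otherwise the cost is one further Cox fit and the loss of some follow-up that could not have contained an event. The change should be made before the data are analysed, so that the censoring of the primary test is not chosen afterwards.

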2 BACKGROUND AND JUSTIFICATION

The use of ICDs in patients who have survived an episode of sudden cardiac arrest (SCA) or sustained ventricular tachycardia (VT) is well established. However, the use of ICDs in patients without a history of SCA or sustained VT episode but at high risk of such an episode is less established in some geographies. The prevention of sudden cardiac death is an important goal, and the ICD plays a vital role by terminating sudden or unexpected arrhythmias leading to sudden cardiac arrest.

Secondary prevention refers to the use of ICDs for the prevention of sudden cardiac death in patients who have survived a prior sudden cardiac arrest or sustained VT, whereas primary prevention refers to the use of ICDs in individuals who are at risk for, but have not yet had a documented episode of sustained VT, VF, or resuscitated cardiac arrest.

The intent of the Improve SCA study is to examine four risk factors in primary prevention patients which may be associated with a higher risk of SCA, thus forming a '1.5 prevention' patient group. These 1.5 criteria are: syncope or pre-syncope, very low ejection fraction (LVEF <25%), non-sustained ventricular tachycardia (NSVT), and frequent premature ventricular contractions (PVCs). The results of this study may be beneficial in helping clinicians identify and refer the highest-risk primary prevention patients for ICDs, help local societies expand guidelines to include primary prevention of SCA utilizing ICDs, and provide additional local evidence to allow patients to make an informed decision whether to receive an ICD.

The 1.5 prevention criteria were developed in 2008 in collaboration with physicians in China to assist in the identification of primary prevention patients at highest risk of SCA. While each of these factors have been independently associated with an increased risk of LVA and/or SCA, no prospective data have been collected to determine if one or more of these factors in a primary prevention ICD population is associated with an increased likelihood of receiving an appropriate ICD therapy. Furthermore, the geographies represented in the Improve SCA study have been underrepresented in previous primary prevention trials and, thus, there are limited local data demonstrating the benefit of ICDs in these geographies' primary prevention patients.

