12.2.6 Sample Size

A simulation program was written to determine the sample size for the study.

Assumptions are based on the OMNI data and estimates from steering committee physicians:

- 60% of enrollments will be secondary prevention and 40% primary prevention
- 50% of primary subjects will be in the 1.5 group
- 57% of secondary subjects will get an ICD (includes CRT-D)
- 45% of 1.5 subjects will get an ICD
- 22% of 1.0 subjects will get an ICD
- Annual attrition (includes exits and deaths) will be 10%
- The study will end two years after the last enrollment

- 4000 patients will take 2 years to enroll with enrollment beginning slowly, then accelerating to a steady 246 per month.
- Expected rates of appropriately treated VT/VF in secondary subjects follow Figure 2, with a higher rate in the first year (22.5%), then a constant rate (11.1%) thereafter.
- The hazard ratio of 1.5 to secondary is 0.91

Under the above assumptions and using the hypothesis test stated above, 4800 subjects will have 80% power to reject the null hypothesis. With 4800 enrolled patients, it is expected that approximately 1650 secondary prevention subjects will be implanted, 430 1.5 prevention subjects will be implanted, and 200 1.0 subjects will be implanted.

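### The sample size re-estimation keeps the OMNI-based VT/VF event rates fixed, so its power figure cannot respond to the event rate in this study; a pooled rate could be added cheaply.

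*SAP*

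**What the plan says.** The planning statement in SAP 3.2 is that "4800 subjects will have 80% power to reject the null hypothesis". It rests on two kinds of input. The group shares and implant rates are steering committee estimates (SAP Appendix). The event rates come from OMNI: "Expected rates of appropriately treated VT/VF in secondary subjects follow Figure 2, with a higher rate in the first year (22.5"%), then 11.1% a year. So does the relative effect: "The hazard ratio of 1.5 to secondary is 0.91". Comments in the simulation program confirm that the rates were chosen to match OMNI.

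The re-estimation repeats the simulation, "using the same simulation methods, but changing the following assumptions using the study data". Seven items follow: the share of secondary subjects, the share of primary subjects who are 1.5, three implant rates, attrition, and enrollment rate. Protocol 12.2.7 has the same list. Neither the VT/VF rates nor the hazard ratio is on it. On type I error the SAP says: "Because no comparisons will be done at the point of re-estimation, alpha is not affected".

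On the result, the sponsor may raise the sample size to at most 8000, lower it, or lengthen or shorten follow-up. Protocol 12.1 plans no data analysis before study completion. The power safeguard in Protocol 12.2.4 is a minimum of 400 implanted 1.5 subjects; it counts subjects, not events.

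**The concern.** The power of a Cox comparison depends on the number of first events. Enrollment, implant rates, attrition and follow-up all act through that number, and so does the event rate. The re-estimation refreshes the former and takes the latter from another study.

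If the rate here were lower than in OMNI, the re-run would still report power computed at 22.5% and 11.1%. Nothing else in the plan would show the shortfall while sample size or follow-up could still be changed. The final confidence interval would show it, but too late to act. The same clause also permits a cut in sample size or follow-up, so a re-run that ignores events could support a reduction in a study already short of them.

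The remedy looks compatible with the plan's own reasoning. A rate pooled over groups A and C compares nothing, so the stated reason for leaving alpha alone covers it.

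**Working it through.** **Inputs.** All from SAP 3.2 and its Appendix unless stated: 60% secondary; 50% of primary subjects are 1.5; implant rates 57% and 45%; attrition 10% a year; enrollment over 2.24 years for 4800 subjects; 2 years of follow-up after the last enrollment; event probabilities 22.5% then 11.1%; hazard ratio 0.91. The alternative is "Hazard ratio of Implanted 1.5 patients to implanted secondary patients > 0.70", tested at one-sided 0.05 by the lower limit of the 90% interval.

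**1. Reproduce the plan's figure.**
- Implanted secondary: 4800 × 0.60 × 0.57 = 1642 (plan: about 1650).
- Implanted 1.5: 4800 × 0.40 × 0.50 × 0.45 = 432 (plan: about 430).
- A re-implementation of the SAP program, 10,000 runs: power 80.7%, mean hazard ratio 0.903 (plan: 80.4% and 0.903). The rows for 4000, 4400 and 5000 also agree to within 1 point.
- Expected first events: 534 in A and 129 in C, 663 in all.

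Cross-check by Schoenfeld's formula, with C share p = 432/2074 = 0.208:

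power = Φ(√(D·p·(1−p)) × ln(0.91/0.70) − 1.645) = Φ(√(663 × 0.208 × 0.792) × 0.262 − 1.645) ≈ Φ(1.10) = 86%.

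This is optimistic. The program applies 0.91 to yearly probabilities, which gives a mean hazard ratio of 0.903, and the allocation is very unequal. The simulation is the right yardstick. The stated 80% is correct on its own inputs.

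**2. Change only the event rate.** The documents give no rate other than OMNI's, so the multiplier is an assumption, shown as a range. Sample size is 4800 with 2-year follow-up. Where a range is given, it spans independent simulation runs.

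| Hazard multiplier | First events, about | Power | Power the planned re-run would report |
|---|---|---|---|
| 1.0 | 662 | about 80% | about 80% |
| 0.8 | 552 | 73-74% | about 80% |
| 0.67 | 474 | 68-71% | about 80% |
| 0.5 | 366 | 58-61% | about 80% |

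With both yearly probabilities multiplied by 1.2, power is about 85%.

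**3. Can the plan's levers respond?** At 0.8, 3 years of follow-up after the last enrollment gives about 80%. At 0.67, 4 years gives 78-80%, or 6600 subjects gives about 81%. With the yearly probabilities halved, about 8000 subjects, the cap, are needed.

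**4. What could be seen at the freeze?** Among 2000 enrolled, A + C implants are 2000 × (0.60 × 0.57 + 0.40 × 0.50 × 0.45) = 684 + 180 = 864, before the SAP 3.1.2 exclusions. Events reach the database only through interrogations: 6-monthly visits, or 3-monthly CareLink transmissions where possible (Protocol 6.10). The relative standard error of a rate from D events is about 1/√D.

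| Observation | Events at 1.0 (rel. SE) | Events at 0.67 (rel. SE) |
|---|---|---|
| Continuous | 116 (9.3%) | 80 (11.2%) |
| 3-monthly | 95 (10.3%) | 65 (12.4%) |
| 6-monthly | 74 (11.6%) | 51 (14.0%) |

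Distance from plan with 6-monthly interrogation, as (expected − observed)/√expected:
- 0.67: (74 − 51)/8.6 = 2.7 standard errors.
- 0.8: (74 − 59)/8.6 = 1.7.
- 0.9: (74 − 67)/8.6 = 0.8.

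Only about 4 of the 116 events fall after month 12, and fewer than 1 with 6-monthly interrogation. The 11.1% rate cannot be estimated separately at that time.

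**The case against.** The omission follows the plan's stated purpose. The re-estimation exists because most inputs were investigator opinion; the VT/VF rate was fitted to observed data. Protocol 12.1 defers analysis to study completion, and Appendix C justifies having no data monitoring committee partly by the absence of an interim test of the primary objective. This explains the omission and means there is no internal contradiction. It does not show that the OMNI rate applies here. A pooled rate tests nothing, so the Appendix C reasoning would still hold.

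A reader might infer that the event rate here is lower and the study underpowered. The documents do not support that. Protocol 2 says that "the geographies represented in the Improve SCA study have been underrepresented in previous primary prevention trials", but that concerns primary prevention trials. The 22.5% and 11.1% are secondary prevention rates, and secondary subjects supply 534 of 663 expected events (81%). The rate could equally be higher.

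A reader might also infer that the event rate is the only unchecked driver. It is not: the hazard ratio of 0.91 is also an OMNI value, and at the planned rate a true ratio of 0.88 gives about 69% power and 0.95 about 93%. Leaving it unchecked is appropriate, because updating it would be a comparison. The fix therefore does not protect power in full.

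The limit on precision also stands. A count of 116 assumes continuous observation; with real interrogation schedules a 10-20% shortfall would not be reliably seen.

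**Conclusion.** The point holds as a cheap improvement, not as an error in the plan. With its other inputs as planned, the re-estimation would report about 80% power regardless of the event rate in this study. Under the assumed multipliers the true figure would be 73-74% at 0.8, 68-71% at 0.67 and 58-61% at 0.5. The loss is gradual, and it affects power only; neither the type I error nor the validity of the confidence interval is touched.

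A pooled check at the planned freeze would carry a relative standard error of about 9-14%, enough to detect a shortfall of about one third. These figures rest on the SAP's own enrollment curve, implant rates and attrition, on a hazard ratio of 0.91, and on one multiplier for all years. It would go too far to say that the sponsor would otherwise fail to act: changes to sample size and follow-up are discretionary either way.

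**What to change.** Add one item to the list in SAP 3.2, and to Protocol 12.2.7 for consistency: *Pooled rate of adjudicated first appropriate VT/VF therapy in groups A and C combined, not split by group, with follow-up censored at the latest interrogation and the hazard ratio held at 0.91.*

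State how it enters the program. One common scaling factor is applied to FAILA12 and FAILALONG, because almost no events after month 12 will be available and the later-year rate cannot be estimated separately. The factor can be the observed number of first events divided by the number expected under the planned rates over the same follow-up. Report its confidence interval, so that a ratio near 1 is not over-read. Since the study is not blinded, say that no event table by group is produced at this step.

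Cost: SAP and protocol wording, including a line reconciling it with Protocol 12.1, and adjudication brought up to date before the freeze; Protocol 6.10.2 already calls for timely episode review. The result may point to longer follow-up or more subjects, which stays at the sponsor's discretion within the 8000 cap. There is no alpha cost, because no groups are compared.
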